5.2.3. Follow-up

Patients will be followed for between 1 and 12 months after the index date. Patients will be censored at the earliest of: 1) disenrollment from insurance coverage; 2) the date of the first claim with a pregnancy diagnosis in the follow-up; 3) the end of data availability on 30 November 2023 or 4) receipt of COVID vaccination. Control patients may be further censored at the date of the first claim with a COVID-19 diagnosis after 30 November 2022.

A sensitivity analysis will be carried out where COVID-19 patients may be further censored at the date of COVID-19 reinfection. This will be further described in the latter part of the study protocol.

5.3. Variables

All data will be extracted from the HealthVerity database; the study measurements are described in detail in Table 1-Table 2. Patient demographic and clinical characteristics will be evaluated at the index date. Comorbid conditions and Charlson Comorbidity Index (CCI) scores will be assessed during the baseline period. Comorbid conditions will be identified by diagnosis codes and/or medication usage. In the default study analysis both the charge and allowed amounts will be evaluated for cost data from the claim database. A sensitivity analysis will be carried out where the paid amounts from the open-source database will be used as the cost data (details described later). HCRU and cost measurements will be evaluated during the baseline and follow-up periods. Intensive care unit (ICU) admission and invasive mechanical ventilation (IMV) will be identified by hospital revenue codes, Healthcare Common Procedure Coding System (HCPCS) procedure codes, and Current Procedural Terminology, 4th Edition (CPT-4) procedure codes.

Table 1. Demographic, Clinical, and Baseline Characteristic Variables

Variable	Role	Data source	Operational definition
Age	Patient characteristic	HealthVerity	Age will be defined at the index date and will be used to assign patients to age groups: Adult (≥18 years): 18 – 29, 30 – 49, 50 – 64, 65 – 74, 75+ years; Pediatric (6 months – < 18 years): 0 – < 2, 2 – 4, 5 – 11, 12 – <18 years. Reported as minimum (min), maximum (max), median (1st – 3rd quartile [Q1-Q3]) and mean (standard deviation [SD]), as well as counts and percentages for age groups.
Gender	Patient characteristic	HealthVerity	Distribution of female and male, unknown patients. Evaluated at the index date and reported as counts and percentages.
State	Patient characteristic	HealthVerity	Distribution of patients' state information. Evaluated at the index date and reported as counts and percentages.
Insurance Type	Patient characteristic	HealthVerity	Distribution of the insurance payer type. Evaluated at the index date and reported as counts and percentages.
Index Year-Month	Patient characteristic	HealthVerity	Year-Month combination of the index date. Evaluated at the index date and reported as counts and percentages.
Site of Index COVID- 19 Diagnosis	Clinical characteristic	HealthVerity	Inpatient, ED/urgent care (UC), Outpatient Non- ED/UC, Other/unknown. Evaluated at the index date and reported as counts and percentages.
Baseline Chronic Medical Conditions (Yes/No)	Clinical characteristic	HealthVerity	Proportions of patients with at least one medical coding for each of the chronic medical conditions listed below during the baseline period (not mutually exclusive) will be identified. Reported as counts and percentages. • Having any of the conditions below

Variable	Role	Data source	Operational definition
Variable	Role	Data source	 ○ Asthma ○ Cancer ○ Cerebrovascular disease ○ Chronic kidney disease ○ Chronic lung diseases limited to: ■ Bronchiectasis ■ COPD (Chronic obstructive pulmonary disease) ■ Interstitial lung disease ■ Pulmonary embolism ■ Pulmonary hypertension ○ Chronic liver diseases limited to: ■ Cirrhosis ■ Non-alcoholic fatty liver disease ■ Alcoholic liver disease ■ Autoimmune hepatitis ○ Cystic fibrosis ○ Diabetes mellitus, type 1 ○ Diabetes mellitus, type 2 ○ Disabilities, including Down syndrome ○ Heart conditions (such as heart failure, coronary artery disease, or cardiomyopathies) ○ Mental health conditions limited to: ■ Mood disorders, including depression ■ Schizophrenia spectrum disorders ○ Neurologic conditions limited to dementia ○ Obesity (BMI >30 kg/m2 or >95th percentile in children) ○ Solid organ or blood stem cell transplantation ○ Tuberculosis Note: racial/ethnic minority status is included in the high risk definition, but not included in Health/verity data and therefore unable to be assessed. Pregnancy is included in the high risk definition, but is an exclusion criteria for each aim in this protocol
			and therefore is not listed here. Given the nature of administrative claims data, obesity islikely to be undercaptured.
Quan-Charlson Comorbidity Index (CCI) Score	Clinical characteristic	HealthVerity	CCI will be defined during the baseline period and will be used to assign patients to CCI groups: 0, 1, 2, 3+. Reported as min, max, median (Q1-Q3) and mean (SD), as well as counts and percentages for CCI groups.
COVID-19 Vaccination Status	Clinical characteristic	HealthVerity	COVID-19 vaccination status (described later) during the baseline period. Categories will be reported as counts and percentages.
Number of All-cause	Patient	HealthVerity	Number of hospitalizations for any cause during the

Variable	Role	Data source	Operational definition
Hospitalization - Baseline	characteristic		baseline period. Reported as min, max, median (Q1-Q3) and mean (SD). The reported numbers will also be assigned to groups: 0, 1, 2, 3+, and reported as counts and percentages. NOTE: in the cases where there is any overlap of place of services, the following hierarchy will be used to determine the place of service: inpatient > emergency department > other outpatient services.
Total Length of Stay (LOS) of All-cause Hospitalization - Baseline	Patient characteristic	HealthVerity	Sum of the LOS (days) of all hospitalizations during the baseline period. Any overlapping inpatient days will be only counted once. Reported as min, max, median (Q1-Q3) and mean (SD).
Total Costs of All- cause Hospitalization - Baseline	Patient characteristic	HealthVerity	Sum of the costs of all hospitalizations during the baseline period. Reported as min, max, median (Q1-Q3) and mean (SD). NOTE: in the cases where there is any overlap of place of services, the following hierarchy will be used to determine the place of service: inpatient > emergency department > other outpatient services.
Number of All-cause Outpatient Visits - Baseline	Patient characteristic	HealthVerity	Number of outpatient visits during the baseline period. Reported as min, max, median (Q1-Q3) and mean (SD). The reported numbers will also be assigned to groups: 0, 1, 2, 3+, and reported as counts and percentages. Same measurements will be reported for the following sub-groups: office visits, emergency department, urgent care claims, others.
Total Costs of All- cause Outpatient Visits - Baseline	Patient characteristic	HealthVerity	Sum of the costs of all outpatient visits during the baseline period. Reported as min, max, median (Q1-Q3) and mean (SD). Same measurements will be reported for the following sub-groups: office visits, emergency department, urgent care claims, others.
Number of All Pharmacy Claims – Baseline	Patient characteristic	HealthVerity	Number of pharmacy claims during the baseline period. Reported as min, max, median (Q1-Q3) and mean (SD).
Total Costs of All Pharmacy Claims - Baseline	Patient characteristic	HealthVerity	Sum of the costs of all pharmacy claims during the baseline period. Reported as min, max, median (Q1-Q3) and mean (SD).
Total Costs of All Healthcare Claims - Baseline	Patient characteristic	HealthVerity	Sum of the costs of all healthcare, including inpatient, outpatient and pharmacy claims during the baseline period. Reported as min, max, median (Q1-Q3) and mean (SD).

Table 2. Follow-up Variables

Variable	Role	Data source	Operational definition
COVID-19 Hospitalization Status Within 30 Days (Yes/No)	Follow-up	HealthVerity	Whether patients had any inpatient COVID-19 hospitalizations within the 30-day period after the index date. Categories of Yes/No reported as counts and percentages.
Follow-up Duration	Follow-up	HealthVerity	Duration of the follow-up period (months). Reported as min, max, median (Q1-Q3) and mean (SD).
All-cause Hospitalization - Follow-up (Yes/No)	Outcome	HealthVerity	Proportions of patients with all-cause hospitalizations during the follow-up period. Reported as counts and percentages.
Number of All-cause Hospitalizations - Follow-up	Outcome	HealthVerity	Number of hospitalizations for any cause during the follow-up period. Reported as min, max, median (Q1-Q3) and mean (SD).
Total LOS of All-cause Hospitalizations - Follow-up	Outcome	HealthVerity	Sum of the LOS of all hospitalizations during the follow-up period. Any overlapping inpatient days will only be counted once. Reported as min, max, median (Q1-Q3) and mean (SD).
Total Costs of All- cause Hospitalizations - Follow-up	Outcome	HealthVerity	Sum of the costs of all hospitalizations during the follow-up period. Reported as min, max, median (Q1-Q3) and mean (SD).
All-cause Outpatient Visits - Follow-up (Yes/No)	Outcome	HealthVerity	Proportions of patients with all-cause outpatient visits during the follow-up period. Reported as counts and percentages.
Number of All-cause Outpatient Visits - Follow-up	Outcome	HealthVerity	Number of outpatient visits during the follow-up period. Reported as min, max, median (Q1-Q3) and mean (SD). Same measurements will be reported for the following sub-groups: office visits, emergency department, urgent care claims, others.
Total Costs of All- cause Outpatient Visits - Follow-up	Outcome	HealthVerity	Sum of the costs of all outpatient visits during the follow-up period. Reported as min, max, median (Q1-Q3) and mean (SD). Same measurements will be reported for the following sub-groups: office visits, emergency department, urgent care claims, others.
All Pharmacy Claims - Follow-up (Yes/No)	Outcome	HealthVerity	Proportions of patients with any pharmacy claims during the follow-up period. Reported as counts and percentages.
Number of All Pharmacy Claims – Follow-up	Outcome	HealthVerity	Number of pharmacy claims during the follow-up period. Reported as min, max, median (Q1-Q3) and mean (SD).
Total Costs of All Pharmacy Claims - Follow-up	Outcome	HealthVerity	Sum of the costs of all pharmacy claims during the follow-up period. Reported as min, max, median (Q1-Q3) and mean (SD).
Total Costs of All Healthcare Claims - Follow-up	Outcome	HealthVerity	Sum of the costs of all healthcare, including inpatient, outpatient and pharmacy claims during the follow-up period. Reported as min, max, median (Q1-Q3) and mean (SD).
Number of COVID-19 Outpatient Visits -	Outcome	HealthVerity	Number of COVID-19 related outpatient visits during the follow-up period. COVID-19-related

SAP version 1.0, 30 May 2024

Variable	Role	Data source	Operational definition
Follow-up			outpatient visits are identified by an outpatient visit diagnosis of COVID-19 in any position. Reported as min, max, median (Q1-Q3) and mean (SD). The same measurements will be reported for the following sub-groups: office visits, emergency department, urgent care claims, others.
Total Costs of COVID- 19 Outpatient Visits - Follow-up	Outcome	HealthVerity	Sum of the costs of COVID-19 related outpatient visits during the follow-up period. COVID-19-related outpatient visits are identified by an outpatient visit diagnosis of COVID-19 in any position. Reported as min, max, median (Q1-Q3) and mean (SD). The same measurements will be reported for the following sub-groups: office visits, emergency department, urgent care claims, others.
Number of COVID-19 Hospitalization - Follow-up	Outcome	HealthVerity	COVID-19-related hospitalizations during the follow-up period. COVID-19 hospitalizations are identified by a hospital discharge diagnosis of COVID-19 in any position. Reported as min, max, median (Q1-Q3) and mean (SD).
Total LOS of COVID-19 Hospitalization - Follow-up	Outcome	HealthVerity	Sum of the LOS of COVID-19-related hospitalizations during the follow-up period. Any overlapping inpatient days will only be counted once. Reported as min, max, median (Q1-Q3) and mean (SD).
Total Costs of COVID- 19 Hospitalization - Follow-up	Outcome	HealthVerity	Sum of the costs of COVID-19-related hospitalizations during the follow-up period. Reported as min, max, median (Q1-Q3) and mean (SD).
COVID-19 Hospitalization Status (Yes/No) - Follow-up	Outcome	HealthVerity	Proportions of patients with or without COVID-19- related hospitalizations during the follow-up period. Reported as counts and percentages.
Total Costs of COVID- 19 Medical Claims - Follow-up	Outcome	HealthVerity	Sum of the costs of all COVID-19-related medical claims, including inpatient and outpatient medical claims during the follow-up period. Reported as min, max, median (Q1-Q3) and mean (SD).
IMV (Yes/No) – Within 30 Days	Outcome	HealthVerity	Proportions of patients with IMV (i.e., intubation and MV, extracorporeal membrane oxygenation [ECMO]) usage during the first 30 days of the follow-up period, among patients with any hospitalizations in the follow-up period. IMV will be identified by HCPCS and CPT-4 procedure codes. Reported as counts and percentages.
IMV Usage Duration – Within 30 Days	Outcome	HealthVerity	Number of days of IMV usage during the first 30 days of the follow-up period. Reported as min, max, median (Q1-Q3) and mean (SD).
ICU Admission (Yes/No) – Within 30 Days	Outcome	HealthVerity	Proportions of patients with ICU admission during inpatient admissions during the first 30 days of the follow-up period, among patients with any hospitalizations in the follow-up period. ICU admission will be identified by hospital revenue

Variable Operational definition Role **Data** source codes, HCPCS, and CPT-4 procedure codes. Reported as counts and percentages. ICU Duration - Within Outcome **HealthVerity** Number of days of ICU stay during the first 30 days of the follow-up period. Reported as min, max, 30 Days median (Q1-Q3) and mean (SD). IMV (Yes/No) - Entire Outcome Proportions of patients with IMV (i.e., intubation and **HealthVerity** MV, extracorporeal membrane oxygenation Follow-up [ECMO]) usage during the follow-up period, among patients with any hospitalizations in the follow-up period. IMV will be identified by HCPCS and CPT-4 procedure codes. Reported as counts and percentages. IMV Usage Duration -Outcome **HealthVerity** Number of days of IMV usage during the follow-up Entire Follow-up period. Reported as min, max, median (Q1-Q3) and mean (SD). ICU Admission Outcome HealthVerity Proportions of patients with ICU admission during (Yes/No) - Entire inpatient admissions within the follow-up period, Follow-up among patients with any hospitalizations in the follow-up period. ICU admission will be identified by hospital revenue codes, HCPCS, and CPT-4 procedure codes. Reported as counts and percentages. ICU Duration- Entire Outcome HealthVerity Number of days of ICU stay during the follow-up Follow-up period. Reported as min, max, median (Q1-Q3) and mean (SD). Oxygen Outcome HealthVerity Proportions of patients with oxygen Supplementation supplementation during the follow-up period, (Yes/No) among patients with any hospitalizations in the follow-up period. Oxygen supplementation will be identified by HCPCS and CPT-4 procedure codes. Reported as counts and percentages. **HealthVerity** Number of days of oxygen supplementation during Oxygen Outcome Supplementation the follow-up period. Reported as min, max, median Duration (Q1-Q3) and mean (SD). Proportions of patients with antiviral COVID drug Antiviral COVID Drug Outcome **HealthVerity** Usage Within 30 Days use within the 30-day period after the index date. After the Index Date Reported as counts and percentages. (Yes/No) COVID-19 Reinfection HealthVerity Proportions of patients with COVID-19 reinfection Outcome during the follow-up period. The COVID-19 (Yes/No) - Follow-up reinfection is defined as another COVID-19 diagnosis at least 90 days after the previous COVID-19 diagnosis. Reported as counts and percentages. Time to COVID-19 HealthVerity Outcome Days from the index date to the first claim date of Reinfection - Follow-up COVID-19 reinfection during the follow-up period. Reported as min, max, median (Q1-Q3) and mean All-cause Mortality **HealthVerity** Proportions of patients with all-cause mortality Outcome (Yes/No) during the index hospitalization or the follow-up

Variable	Role	Data source	Operational definition
			period. Reported as counts and percentages. Note: Death information is available and is sourced from over 40,000 public and private sources nationally. The coverage rate, estimated at over 90% of CDC reported deaths through present day, is based on the number of deaths in the Fact of Death Mortality Index compared to the number of deaths reported by the CDC. Due to HIPAA privacy restrictions, date of death is reported as month and year. Cause of death is not available.

COVID-19 Vaccination Status:

The exposure of interest is the BNT162b2 Bivalent vaccine.

A patient will be considered vaccinated from 14 days after their vaccination date.

The source of the exposure variables are the California and Louisiana vaccine registries and the HealthVerity claims database. Clinical Vaccines Administered code (CVX), National Drug Codes (NDC) and Current Procedural Terminology® (CPT) codes.

BNT162b2 Bivalent vaccinations will be enumerated using the following hierarchical definition:

- Any person in HealthVerity claims data who has a record in the California/Louisiana Immunization Registry with a CVX code indicating having received the BNT162b2 Bivalent vaccine will be considered vaccinated 14 days after registry event date.
- 2. Any person in HealthVerity claims data who does not have a record in the California/Louisiana Immunization Registry but has a pharmacy claim with an NDC code indicating an BNT162b2 Bivalent vaccine dose will be considered vaccinated 14 days after claim date.
- 3. Any person in HealthVerity claims data who does not have a record in the California/Louisiana Immunization Registry and does not have a pharmacy claim with an NDC code indicating an BNT162b2 Bivalent vaccine dose but has a medical claim with a CPT code indicating an BNT162b2 Bivalent vaccine dose will be considered vaccinated 14 days after claim date.

4. Any person in HealthVerity claims data who does not have a record in the California/Louisiana Immunization Registry, does not have a pharmacy claim with an NDC code indicating an BNT162b2 Bivalent vaccine dose and does not have a medical claim with a CPT code indicating an BNT162b2 Bivalent mRNA vaccine dose will be considered BNT162b2 Bivalent unvaccinated.

Patients will be categorized into the following groups based on their COVID-19 vaccination status:

- BNT162b2 Bivalent mRNA Vaccine: Patients who received at least one dose of a BNT162b2 Bivalent mRNA vaccine in the baseline period, at least 14 days prior to the index date.
- No Vaccine: Patients who did not receive any COVID-19 vaccines in the up to 12 months prior to the index date. For patients with baseline periods of less than 12 months, all available records in the past up to 12 months periods will be searched.
- Other Vaccines: Patients who were not in the above described 2 vaccination groups. They may include patients who received any type of COVID-19 vaccine in the up to 12 months prior to index date, but did not meet the BNT162b2 Bivalent Vaccine group requirements described above. Some examples of these include patients 1) who had other types of mRNA COVID-19 vaccine and no doses of a BNT162b2 Bivalent vaccine in the baseline period; 2) who received non-mRNA vaccines, etc.

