8.3. Variables

TABLE 3. EXPOSURE VARIABLES

Variable	Data source(s)	Operational definition
BNT162b2 XBB.1.5 mRNA vaccine after FDA authorization date and 14 or more days	California/Louisiana Immunization Registry as well as HV Claims	Vaccines will be enumerated as per section 8.2. Date of vaccination will be used to assess time-based inclusion/exclusion criteria.
BNT162b2 BA.4/5 mRNA vaccine after FDA authorization date and 14 or more days	California/Louisiana Immunization Registry as well as HV Claims	Vaccines will be enumerated as per section 8.2. Date of vaccination will be used to assess time-based inclusion/exclusion criteria.
Influenza vaccine	HV Claims	Identified using NDC or CPT code

TABLE 4. OUTCOME VARIABLES

Variable	Data source(s)	Operational definition
COVID-19 diagnosis	HV Claims	Any encounter regardless of diagnosis position or setting with ICD-10-CM code: U07.1
COVID-19 hospitalization	HV Claims	Inpatient encounter at an acute care facility with ICD-10-CM code: U07.1 "COVID-19" listed in any diagnosis position
COVID-19 emergency department visit	HV Claims	Emergency department visit with ICD-10-CM code: U07.1

Variable	Data source(s)	Operational definition
COVID-19 outpatient encounter	HV Claims	Outpatient encounter with ICD-10-CM code: U07.1
COVID-19 critical illness	HV Claims	Intensive care unit [ICU] admission, mechanical ventilation, or inpatient death
All-cause mortality	HV Mortality Database	HealthVerity ID in Mortality Database
Non-COVID-19 respiratory infections (pneumonia, RSV, rhinovirus, antibiotic prescriptions)	HV Claims	Any encounter regardless of setting with ICD-10- CM code for diagnosis or NDC codes for antibiotics (Codes in Annex)
Hospitalization length of stay (days)	HV Claims	Date of service end – date of service
ICU admission	HV Claims	As per HealthVerity's suggestion, ICU related services/inpatient stays will be found on Institutional claims, and can be identified using revenue codes (codes in Annex).
Invasive ventilation	HV Claims	CPT, HCPCS and ICD-10 (codes in Annex)
Cost of hospitalization	HV Claims	Using HealthVerity's "Proxy Financial Algorithm", based on CMS Medicare prospective payment system fee schedules
Influenza diagnosis	HV Claims	Any encounter regardless of setting with ICD-10- CM code: J09-J11
Influenza hospitalization	HV Claims	Inpatient encounter with ICD-10-CM code: J09- J11 listed as in any diagnosis position

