5.2.1.1. Aim 3B Adult Inclusion Criteria

- 1. Born in 2004 or earlier (as age 18 or older as of the index date, owing to the data providing year but not month or day of birth).
- 2. Has COVID-19 diagnosis (ICD-10-CM code U07.1) in any setting, any position between 01 June 2022 and 30 November 2022 (first eligible code is the index date).
- 3. At least one year of continuous pharmacy and medical enrollment in HealthVerity prior to index date (ie, COVID-19 diagnosis). A gap of up to 30 days will be allowed.
- 4. Have been a State of California/Louisiana resident for at least one year prior to index date (ie, COVID-19 diagnosis)
- 5. Have continuous medical and prescription insurance coverage for at least 30 days after the index date (follow-up period).
 - The duration of the follow-up period will be required to be at least 1 month.
 - NOTE: since the evaluation of the long-term HCRU and cost starts from 1 month after the index date, this requirement for patients to have at least one month of follow-up is needed for this study.

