5.6. Data Analyses

Descriptive statistics will be utilized to summarize patient demographic and clinical characteristics in addition to the measured HCRU and cost outcomes. Counts and percentages will be reported for categorical variables. Continuous variables will be summarized using minimum, maximum, median (Q1-Q3) and mean (SD).

All cost measurements will be adjusted to 2024 USD using Consumer Price Index medical care component.

All study measurements will be compared between the COVID-19 and Control cohorts.

HCRU and Cost Outcomes at Different Time Periods:

For HCRU and cost outcomes, all measurements will be provided for the following time periods:

- Post-acute phase: 1-11 months (measured starting from 30 days after the index date)
 - 1 to <2 months (1 month post-acute period)
 - 1 to <4 months (3 month post-acute period)
 - 1 to <7 months (6 month post-acute period)
 - 1 to <10 months (9 month post-acute period)
 - 1 to <12 months (11 month post-acute period)

Within this study, 1 month is generally considered to be equivalent to 30 days, unless otherwise specified.

NOTE: HCRU and cost will not be measured during the acute phase of 0 to <1 month after the index date since this is not within the study scope.

Stratification Analysis:

Patients will be further stratified by the following variables:

Age group:

 Among the overall study population, patients will be stratified by their age at the index date as follows:

- Adult and Pediatric
 - Adult: Patients ≥ 18 years at the index date.
 - Pediatric: Patients 6 months to < 18 years at the index date.
- Detailed Age Groups
 - Adult: 18 29, 30 49, 50 64, 65 74, 75+ years
 - Pediatric: 0 < 2, 2 4, 5 11, 12 < 18 years.
- COVID-19 Vaccination Status:
 - BNT162b2 Bivalent mRNA Vaccine
 - No Vaccine
 - NOTE: Other Vaccines sub-group for vaccination status will not be used for this stratification analysis.
- Site of Care: COVID-19 Hospitalization Status Within 30 Days (Yes/No):
 - Yes
 - No
- ICU Admission (Yes/No) Within 30 Days:
 - Among the overall study population, patients will be stratified by status of ICU Admission (Yes/No) – Within 30 Days
- IMV Usage (Yes/No) Within 30 Days:
 - Among the overall study population, patients will be stratified by status of IMV usage (Yes/No) – Within 30 Days

Sensitivity Analysis:

Sensitivity analyses planned for the study will include:

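### Aim 3B SAP, Table 2: the two 30-day ICU and IMV percentages are taken over patients hospitalized at any time in follow-up, so they are diluted and depend on follow-up length

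*SAP*

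**What the plan says.** Table 2 of the Aim 3B SAP (5.3 Variables) has four ICU and IMV rows confined to the first 30 days: a Yes/No row and a duration row for each. The ICU Yes/No row counts "ICU admission during inpatient admissions during the first 30 days of the follow-up period, among patients with any hospitalizations in the follow-up period". The IMV Yes/No row counts "usage during the first 30 days of the follow-up period, among patients with any hospitalizations in the follow-up period". The two duration rows name no population. The Yes/No rows for the entire follow-up use the same denominator.

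On follow-up, SAP 5.2.3 says "Patients will be followed for between 1 and 12 months after the index date". The adult inclusion criteria (5.2.1.1) treat the first month as part of it: "Have continuous medical and prescription insurance coverage for at least 30 days after the index date (follow-up period". Follow-up ends early at disenrollment, a pregnancy claim or COVID-19 vaccination, and in addition "Control patients may be further censored at the date of the first claim with a COVID-19 diagnosis after 30 November 2022". On use, SAP 5.6 says "All study measurements will be compared between the COVID-19 and Control cohorts", and it also plans stratification by age, vaccination status, and 30-day COVID-19 hospitalization, ICU and IMV status.

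On IMV codes, Protocol Table 4 (8.3) lists "CPT, HCPCS and ICD-10 (codes in Annex". SAP Table 2 says "IMV will be identified by HCPCS and CPT-4 procedure codes". The text of SAP 5.3 lists hospital revenue codes, HCPCS and CPT-4 for ICU and IMV together.

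**The concern.** A 30-day ICU or IMV percentage among hospitalized patients will be read as a measure of acute severity. As defined, it mixes two windows. Someone not admitted in the first month but admitted for an unrelated reason in month 8 is in the denominator and cannot be in the numerator. The result then depends on how many later first admissions were observed, and so on how long patients stayed under observation.

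Two groups with the same acute experience can therefore show different percentages. Controls carry an extra censoring rule. They also have no index illness that concentrates admissions in the first month, so dilution is likely to be heavier for them even when follow-up is equal. The case-control comparison of these rows would partly reflect the denominator.

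The IMV code sources are a separate matter. A code list that misses ventilation would class those patients as No, both in the row and in the IMV stratification.

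**Working it through.** **Step 1: set the windows side by side.**

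| Row (Aim 3B SAP, Table 2) | Numerator window | Denominator window |
|---|---|---|
| ICU Yes/No, 30 days | days 0–30 | whole follow-up, 1–12 months |
| IMV Yes/No, 30 days | days 0–30 | whole follow-up, 1–12 months |
| ICU and IMV Yes/No, entire follow-up | whole follow-up | whole follow-up |
| ICU and IMV duration, 30 days | days 0–30 | none stated |

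The windows disagree only in the first two rows.

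**Step 2: consequence.** The plan states no figure for these proportions, so there is none to reproduce. Let *h* be the share hospitalized in days 0–30, *q* the ICU (or IMV) share among them, *r* the monthly hazard of a first hospitalization after day 30, and *L* the months of follow-up. Then

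reported proportion = *q·h* / [*h* + (1 − *h*)(1 − exp(−*r*(*L* − 1)))].

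At *L* = 1 this equals *q*. For any *r* above zero it falls as *L* grows. With the denominator limited to patients hospitalized in days 0–30, it equals *q* at every *L*.

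**Step 3: illustration.** All rates are assumptions, with *q* = 20% throughout. For *h* = 5%, *r* = 0.5% per month and *L* = 12:

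- later first admissions: 0.95 × (1 − exp(−0.055)) = 0.0508
- reported: 0.20 × 0.05 / (0.05 + 0.0508) = 0.010 / 0.1008 = 9.9%

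| Assumed *h*, *r* | 1 mo | 3 mo | 6 mo | 9 mo | 12 mo |
|---|---|---|---|---|---|
| 5%, 0.5% | 20.0% | 16.8% | 13.6% | 11.5% | 9.9% |
| 10%, 0.5% | 20.0% | 18.4% | 16.4% | 14.8% | 13.5% |
| 2%, 0.5% | 20.0% | 13.4% | 9.1% | 6.8% | 5.5% |
| 5%, 1% | 20.0% | 14.5% | 10.4% | 8.1% | 6.7% |
| 2%, 1% | 20.0% | 10.2% | 5.9% | 4.2% | 3.3% |
| 0.5%, 0.5% (control-like) | 20.0% | 6.7% | 3.4% | 2.3% | 1.7% |
| Matched denominator, any row | 20% | 20% | 20% | 20% | 20% |

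Over the case-like rows the 12-month range is 3.3% to 13.5%. Against a 9.9% case figure, a control-like cohort would show 1.7% at 12 months, or 3.4% if followed for 6 months, although the true share is 20% in both.

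**Step 4: IMV codes.** Protocol Table 4 has CPT, HCPCS and ICD-10. SAP 5.3 text has revenue codes, HCPCS and CPT-4. SAP Table 2 has HCPCS and CPT-4. These are three different source lists, and the SAP gives no reason for the differences. The Aim 3B SAP uses ICD-10-PCS codes in its immunosuppression exclusion (5.2.2), so ICD-10 procedure codes are evidently available.

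**The case against.** The strongest reply is that little depends on these two rows, and that the useful figures can largely be had elsewhere. SAP 5.6 stratifies by COVID-19 hospitalization within 30 days. Everyone in the Yes stratum is in the denominator whatever happens later, so the ICU and IMV shares there are undiluted. The same section splits the overall population by 30-day ICU and IMV status, so stratum sizes give the full-cohort proportion. Acute-phase utilization and cost are declared out of scope, and no regression outcome uses ICU or IMV. All of this stands. It does not repair the overall rows, 30-day admissions not counted as COVID-19, or the comparison with controls.

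Several stronger readings are tempting but unsupported:

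- That all four 30-day rows have the wrong denominator. Only the two Yes/No rows state one; the duration rows need a population specified.
- That the regressions or the ICU and IMV strata are distorted by the denominator. The regression outcomes are counts and costs of admissions and claims, and the strata are formed in the overall population.
- That controls are diluted about twelvefold. That needs an even admission rate and a full 12 months of follow-up for everyone; with censoring it is a ceiling under that assumption.
- That omitting ICD-10 breaches the protocol. Protocol 8.7 lets the SAP modify the plan, Table 4 serves all aims, and the protocol's Aim 3B outcome list does not name IMV. Table 4 does not say whether diagnosis or procedure codes are meant, and the code list is not in the documents reviewed.

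One could also read the denominator as post-acute admissions only, since utilization is measured from day 30 and the mortality row separates the index hospitalization from follow-up. That does not help: a patient in ICU only in month 1 could then be in the numerator but not in the denominator.

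**Conclusion.** The window mismatch is real on the text and should be corrected. The two 30-day percentages are diluted whenever anyone is first hospitalized after day 30, and they move with follow-up length. They can therefore differ between cases and controls, or between strata, without any difference in acute severity.

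The size is unknown because the documents give no hospitalization or ICU rates. Under the assumed rates above, a true 20% becomes about 10% at 12 months in the central case and under 2% in a control-like cohort. These are illustrations, not estimates.

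The reach is limited to two descriptive percentages and their comparisons. The IMV code difference is an unexplained but permitted departure of unknown size. It matters because IMV status is also a stratification variable.

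**What to change.** 1. In the two 30-day Yes/No rows of Table 2, set the denominator to patients hospitalized within 30 days of index, and also report the proportion of the full cohort. Leave the denominator of the entire-follow-up rows as it is.
2. State the population for the two 30-day duration rows.
3. State in Table 2 that follow-up starts at the index date and whether the index hospitalization belongs to it, so that the mortality row and the ICU and IMV rows agree.
4. Use one IMV code list across SAP 5.3 text and Table 2, reconciled with Protocol Table 4. Include the ICD-10 source or give the reason for leaving it out, and settle whether revenue codes identify IMV.

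The cost is SAP and table-shell wording plus a small programming change. No new data are needed.
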